## 12.10. Appendix 10: Abbreviations & Trade Marks

### 12.10.1. Abbreviations

Abbreviation	Description
1-RM	1 repetition maximum
AP	Analysis Population
A&R	Analysis and Reporting
ADaM	Analysis Data Model
AE	Adverse Event
AIC	Akaike's Information Criteria
BDRM	Blinded data review meeting
BP	Blood Pressure
BS	Biostatistics
CAT	COPD Assessment Test
CDISC	Clinical Data Interchange Standards Consortium
CI	Confidence Interval
COPD	Chronic Obstructive Pulmonary Disease
CPMS	Clinical Pharmacology Modelling & Simulation
CRF	Case report form
CS	Clinical Statistics
CSR	Clinical Study Report
CTR	Clinical Trial Register
CV	Cardiovascular
CVA	Cerebrovascular event stroke
CWR	Constant Work Rate
DAP	Data Analysis Plan
DBF	Database Freeze
DBR	Database Release
DM	Data management
DOB	Date of Birth
DP	Decimal Places
DVT	Deep vein thrombosis
DXA	Dual-energy X-ray Absorptiometry
ECG	Electrocardiogram
eCRF	Electronic Case Record Form
EMA	European Medicines Agency
FDA	Food and Drug Administration
FDAAA	Food and Drug Administration Clinical Results Disclosure Requirements
FSH	Follicle-stimulating hormone
GSK	GlaxoSmithKline
HR	Heart rate
IA	Interim Analysis
ICH	International Conference on Harmonization
IDSL	Integrated Data Standards Library
IMMS	International Modules Management System

Abbreviation	Description
IP	Investigational Product
LH	Luteinizing hormone
LVEF	Left ventricular ejection fraction
MMRM	Mixed Model Repeated Measures
MRI	Magnetic Resonance Imaging
PCI	Potential Clinical Importance
PD	Pharmacodynamic
PDMP	Protocol Deviation Management Plan
PE	Pulmonary embolism
PGIC	Patient Global Impression of Change
PGRS	Patient Global Rating of Severity
PSA	Prostate specific antigen
PK	Pharmacokinetic
PP	Per Protocol
QC	Quality Control
QTcB	Bazett's QT Interval Corrected for Heart Rate
QTcF	Frederica's QT Interval Corrected for Heart Rate
RAMOS	Randomization & Medication Ordering System
RAP	Reporting & Analysis Plan
SAC	Statistical Analysis Complete
SARM	Selective Androgen Receptor Modulator
SD	Standard deviation
SDSP	Study Data Standardization Plan
SDTM	Study Data Tabulation Model
SE	Standard error
SGRQ	St George Respiratory Questionnaire
SGRQ-c	St George Respiratory Questionnaire-COPD
SMG	Safety and Medical Governance
SnIP	Sniff Nasal Inspiratory Pressure
SOP	Standard Operation Procedure
SPPB	Short Physical Performance Battery
SRT	Safety Review Team
SHBG	Sex hormone-binding globulin
TA	Therapeutic Area
TFL	Tables, Figures & Listings
TIA	Transient ischemic attack
FEV1	Forced Expiratory Volume in 1 second
SnIP	Sniff Nasal Inspiratory Pressure

**12.10.2. Trademarks**

Trademarks of the GlaxoSmithKline Group of Companies
None

Trademarks not owned by the GlaxoSmithKline Group of Companies
None

## 12.11. Appendix 11: List of Data Displays

### 12.11.1. Data Display Numbering

The following numbering will be applied for RAP generated displays:

Section	Tables	Figures
Study Population	1.1 to 1.13	
Efficacy	2.1 to 2.47	2.1 to 2.9
Safety	3.1 to 3.36	3.1 to 3.4
PK	4.1	
Section	Listings	
ICH Listings	1 to 34	
Other Listings	35 to 89	

### 12.11.2. Mock Example Shell Referencing

Non IDSL specifications will be referenced as indicated and if required example mock-up displays provided in [Appendix 12](#): Example Mock Shells for Data Displays.

Section	Figure	Table	Listing
Study Population	POP_Fn	POP_Tn	POP_Ln
Efficacy	EFF_Fn	EFF_Tn	EFF_Ln
Safety	SAFE_Fn	SAFE_Tn	SAFE_Ln

**NOTES:**

- Non-Standard displays are indicated in the 'IDSL / Example Shell' or 'Programming Notes' column as '[Non-Standard] + Reference.'

### 12.11.3. Deliverables

Delivery	Description
SAC	Final Statistical Analysis Complete

## 12.11.4. Study Population Tables

Study Population Tables					
No.	Population	IDSL / Example Shell	Title	Programming Notes	Deliverable [Priority]
Subject Disposition					
1.1.	All Participants	ES1	Summary of Subject Disposition for the Subject Conclusion Record	ICH E3, FDAAA, EudraCT	SAC
1.2.	All Participants	SD1	Summary of Treatment Status and Reasons for Discontinuation of Study Treatment	ICH E3	SAC
1.3.	Screened	ES6	Summary of Screening Status and Reasons for Screen Failure	Journal Requirements	SAC
1.4.	Enrolled	NS1	Summary of Number of Participant by Country and Site ID	EudraCT/Clinical Operations	SAC
Protocol Deviation					
1.5.	All Participants	DV1	Summary of Important Protocol Deviations	ICH E3	SAC
Population Analysed					
1.6.	Screened	SP1	Summary of Study Populations	IDSL	Headline Results & SAC
1.7.	All Participants	SP2	Summary of Exclusions from the Per Protocol Population	IDSL	SAC
Demographic and Baseline Characteristics					
1.8.	All Participants	DM1	Summary of Demographic Characteristics	ICH E3, FDAAA, EudraCT Footnote: Age is imputed when full date of birth is not provided.	Headline Results & SAC

Study Population Tables					
No.	Population	IDSL / Example Shell	Title	Programming Notes	Deliverable [Priority]
1.9.	Enrolled	DM11	Summary of Age Ranges	EudraCT Footnote: Age is imputed when full date of birth is not provided.	SAC
1.10.	All Participants	DM5	Summary of Race and Racial Combinations	ICH E3, FDA, FDA, EudraCT	SAC
Prior and Concomitant Medications					
1.11.	All Participants	MH4	Summary of Medical Conditions	ICH E3	SAC
1.12.	All Participants	CM1	Summary of Concomitant Medications	ICH E3 Note: On-Treatment phase includes both On-Treatment and Post-Treatment concomitant medications.	SAC
Exposure					
1.13.	Safety	EX1	Summary of Extent of Exposure to Investigational Product	ICH E3	SAC

12.11.5. Efficacy Tables

Efficacy: Tables					
No.	Population	IDSL / Example Shell	Title	Programming Notes	Deliverable [Priority]
Primary Efficacy					
2.1.	Analysis	EFF_T1	Analysis of Percent Change from Baseline in Leg Press Strength (%) by Visit - Repeated Measure Mixed Model		Headline Results & SAC
2.2.	Per Protocol	EFF_T1	Analysis of Percent Change from Baseline in Leg Press Strength (%) by Visit - Repeated Measure Mixed Model		SAC
2.3.	Analysis	EFF_T1	Analysis of Change from Baseline in Leg Press Strength (kg) by Visit - Repeated Measure Mixed Model		SAC
2.4.	Per Protocol	EFF_T1	Analysis of Change from Baseline in Leg Press Strength (kg) by Visit- Repeated Measure Mixed Model		SAC
2.5.	Analysis	EFF_T2	Bayesian Analysis of Percentage Change from Baseline in Leg Press Strength (%) by Visit		Headline Results & SAC
2.6.	Analysis	EFF_T3	Descriptive Summary of Change and Percent Change from Baseline in Leg Press Strength by Visit	Summarize the data for change from baseline, percentage change from baseline and ratio to baseline along with the data at each visit for parameters Last Successful Lift 1-Rep Max (kg), Number of Successful Lifts and Starting Lift Weight (kg).	Headline Results & SAC

2.7.	Per Protocol	EFF_T3	Descriptive Summary of Change and Percent Change from Baseline in Leg Press Strength by Visit	Summarize the data for change from baseline, percentage change from baseline and ratio to baseline along with the data at each visit for parameters Last Successful Lift 1-Rep Max (kg), Number of Successful Lifts and Starting Lift Weight (kg).	SAC
2.8.	Analysis	EFF_T1	Analysis of Percent Change from Baseline in Leg Press Strength (%) by Visit - Repeated Measure Mixed Model with Exploratory Covariate	Add the exploratory covariates predicted FEV1 and BMI at baseline in the same model for Table 2.1. Update the shell footnote by adding the exploratory covariates	SAC
Secondary Efficacy					
2.9.	Analysis	EFF_T1	Analysis of Change from Baseline in Appendicular (kg), and Total Lean Mass (kg) as Assessed by Dual-energy X-ray Absorptiometry by Visit - Repeated Measure Mixed Model	Similar shell as EFF_T1, add a by line for Parameter under the Sex p-value is not required	Headline Results & SAC
2.10.	Analysis	EFF_T1	Analysis of Percent Change from Baseline in Appendicular (%), and Total Lean Mass (%) as Assessed by Dual-energy X-ray Absorptiometry by Visit - Repeated Measure Mixed Model	Similar shell as EFF_T1, add a by line for Parameter under the Sex p-value is not required	SAC
2.11.	Analysis	EFF_T3	Descriptive Summary of Change and Percent Change from Baseline in Appendicular and Total Lean Mass as Assessed by Dual-energy X-ray Absorptiometry by Visit	Summarize the data for change from baseline, percentage change from baseline and ratio to baseline along with the data at each visit	Headline Results & SAC
2.12.	Analysis	EFF_T1	Analysis of Change from Baseline in PROactive Total Score, Difficulty and Amount Scores by Visit- Repeated Measure Mixed Model	Similar shell as EFF_T1, add a by line for Parameter under the Sex p-value is not required	Headline Results & SAC

**CONFIDENTIAL**

200182

2.13.	Per Protocol	EFF_T1	Analysis of Change from Baseline in PROactive Total Score, Difficulty and Amount Scores by Visit- Repeated Measure Mixed Model	Similar shell as EFF_T1, add a by line for Parameter under the Sex p-value is not required	SAC
2.14.	Analysis	EFF_T2	Bayesian Analysis of Change from Baseline in PROactive Total Score by Visit		Headline Results & SAC
2.15.	Analysis	EFF_T3	Descriptive Summary of Change from Baseline in PROactive Total Score, Difficulty and Amount Scores by Visit	Summarize the data for change from baseline and ratio to baseline along with the data at each visit	Headline Results & SAC
2.16.	Per Protocol	EFF_T3	Descriptive Summary of Change from Baseline in PROactive Total Score, Difficulty and Amounts Scores by Visit	Summarize the data for change from baseline and ratio to baseline along with the data at each visit	SAC
2.17.	Analysis	EFF_T1	Analysis of Change from Baseline in COPD Assessment Test (CAT) score by Visit- Repeated Measure Mixed Model	Similar shell as EFF_T1, p-value is not required	SAC
2.18.	Analysis	EFF_T6	Responder Analysis of COPD Assessment Test (CAT)		SAC
2.19.	Analysis	EFF_T3	Descriptive Summary of Change from Baseline in COPD Assessment Test (CAT) score by Visit	Summarize the data for change from baseline and ratio to baseline along with the data at each visit	SAC
2.20.	Analysis	EFF_T7	Analysis of Change from Baseline in St George Respiratory Questionnaire (SGRQ) Total Score and Domains Score at Day 90 - ANCOVA Model		Headline Results & SAC
2.21.	Per Protocol	EFF_T7	Analysis of Change from Baseline in St George Respiratory Questionnaire (SGRQ) Total Score and Domains Score at Day 90 – ANCOVA Model		SAC
2.22.	Analysis	EFF_T6	Responder Analysis of St George Respiratory Questionnaire (SGRQ)		SAC
2.23.	Analysis	EFF_T2	Bayesian Analysis of Change from Baseline in St George Respiratory Questionnaire (SGRQ) Total Score at Day 90	Same as EFF_T2, remove the visit column	Headline Results & SAC

**CONFIDENTIAL**

200182

2.24.	Analysis	EFF_T3	Descriptive Summary of Change from Baseline in St George Respiratory Questionnaire (SGRQ) Total Score and Domains Scores by Visit	Summarize the data for change from baseline and ratio to baseline along with the data at each visit	Headline Results & SAC
2.25.	Per Protocol	EFF_T3	Descriptive Summary of Change from Baseline in St George Respiratory Questionnaire (SGRQ) Total Score and Domains Scores by Visit	Summarize the data for change from baseline and ratio to baseline along with the data at each visit	SAC
2.26.	Analysis	EFF_T1	Analysis of Change from baseline in total Short Physical Performance Battery (SPPB) score and times for chair rise (sec) and 4 m gait speed (sec) by Visit - Repeated Measure Mixed Model	Similar shell as EFF_T1, add a by line for Parameter under the Sex p-value is not required	Headline Results & SAC
2.27.	Per Protocol	EFF_T1	Analysis of Change from baseline in total Short Physical Performance Battery (SPPB) score and times for chair rise (sec) and 4 m gait speed (sec) by Visit - Repeated Measure Mixed Model	Similar shell as EFF_T1, add a by line for Parameter under the Sex p-value is not required	SAC
2.28.	Analysis	EFF_T2	Bayesian Analysis of Change from Baseline in Times for chair rise (sec) by Visit		Headline Results & SAC
2.29.	Analysis	EFF_T3	Descriptive Summary of Change from baseline in total Short Physical Performance Battery (SPPB) score and times for chair rise and 4 m gait speed by Visit	Summarize the data for change from baseline and ratio to baseline along with the data at each visit	Headline Results & SAC
2.30.	Per Protocol	EFF_T3	Descriptive Summary of Change from baseline in total Short Physical Performance Battery (SPPB) score and times for chair rise and 4 m gait speed by Visit	Summarize the data for change from baseline and ratio to baseline along with the data at each visit	SAC
2.31.	Analysis	EFF_T7	Analysis of Change from Baseline in Constant Work Rate (CWR) Duration (sec) from Endurance Shuttle Walking Test at Day 90 – ANCOVA model	Similar shell as EFF_T7, remove the column 'Parameter'	Headline Results & SAC
2.32.	Per Protocol	EFF_T7	Analysis of Change from Baseline in Constant Work Rate (CWR) Duration (sec) from Endurance Shuttle Walking Test at Day 90 – ANCOVA model	Similar shell as EFF_T7, remove the column 'Parameter'	SAC

**CONFIDENTIAL**

200182

2.33.	Analysis	EFF_T7	Analysis of Percent Change from Baseline in Constant Work Rate (CWR) Duration (%) from Endurance Shuttle Walking Test at Day 90 – ANCOVA model	Similar shell as EFF_T7, remove the column 'Parameter' Update footnote [1] as “[1] Lsmeans of percent change from baseline for each treatment group as well as the difference of lsmeans of percent change from baseline is estimated from ANCOVA model with baseline score as the covariate adjusting for the treatment. In case of violation of the assumptions, the same model is fitted with log of ratio to baseline and replacing the covariate baseline with log baseline.”	SAC
2.34.	Analysis	EFF_T2	Bayesian Analysis of Change from Baseline in Constant Work Rate (CWR) Duration (sec) from Endurance Shuttle Walking Test at Day 90	Same as EFF_T2, remove the visit column	Headline Results & SAC
2.35.	Analysis	EFF_T3	Descriptive Summary of Change and Percent Change from Baseline in Constant Work Rate (CWR) Duration from Endurance Shuttle Walking Test by Visit	Summarize the data for change from baseline, percentage change from baseline and ratio to baseline along with the data at each visit	Headline Results & SAC
2.36.	Per Protocol	EFF_T3	Descriptive Summary of Change and Percent Change from Baseline in Constant Work Rate (CWR) Duration from Endurance Shuttle Walking Test by Visit	Summarize the data for change from baseline, percentage change from baseline and ratio to baseline along with the data at each visit	SAC
2.37.	Analysis	EFF_T7	Analysis of Change from Baseline in Peak Performance from Incremental Shuttle Walking Test at Day 90 – ANCOVA Model	Similar shell as EFF_T7, remove the column 'Parameter'	SAC

**CONFIDENTIAL**

200182

2.38.	Analysis	EFF_T7	Analysis of Percent Change from Baseline in Peak Performance from Incremental Shuttle Walking Test (%) at Day 90 – ANCOVA Model	Similar shell as EFF_T7, remove the column 'Parameter' Update footnote [1] as “[1] Lsmeans of percent change from baseline for each treatment group as well as the difference of Lsmeans of percent change from baseline is estimated from ANCOVA model with baseline score as the covariate adjusting for the treatment. In case of violation of the assumptions, the same model is fitted with log of ratio to baseline and replacing the covariate baseline with log baseline.”	SAC
2.39.	Analysis	EFF_T3	Descriptive Summary of Change and Percent Change from Baseline in Peak Performance from Incremental Shuttle Walking Test by Visit	Summarize the data for change from baseline, percentage change from baseline and ratio to baseline along with the data at each visit. Update footnote as “Note: When there are multiple pre-dose assessments, the highest non-missing pre-dose assessment from day -9 and day 1 is identified and captured as "Baseline (Derived)" visit”	SAC
2.40.	Analysis	EFF_T3	Descriptive Summary of Change from Baseline in Physical Activity Measures as Assessed via an Accelerometer.		SAC
2.41.	Analysis	EFF_T8	Descriptive Summary of Patient Global Impression of Change		SAC
2.42.	Analysis	EFF_T10	Descriptive Summary of Patient Global Rating of Severity.		SAC
2.43.	Analysis	EFF_T3	Descriptive Summary of Change from Baseline in FEV1 (L) by Visit	This table will include both FEV1 (L) and Percent Predicted FEV1.	SAC

2.44.	Analysis	EFF_T3	Descriptive Summary of Change from Baseline in Sniff Nasal Inspiratory Pressure (SnIP) by Visit		SAC
Exploratory					
2.45.	Analysis	EFF_T3	Descriptive Summary of Change from Baseline in Handgrip strength	First left hand, then right hand	SAC
2.46.	Analysis	EFF_T5	Descriptive Summary of Change from Baseline in PROactive total and domains scores in different levels of PGIC		SAC
2.47.	Analysis	EFF_T4	Analysis of Change from Baseline in Leg Press Strength (kg) by Visit excluding the site PPD (Impact analysis) - Repeated Measure Mixed Model	Fit the model for Table 2.3 by excluding the site PPD.	SAC

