9.1.2. Day -9 and day 80 visits

The purpose of the day -9 and day 80 visits is primarily to collect 7 days of activity data from the previous visits (screening and day 56 visits respectively) and to dispense activity monitors for the following visit. Activity data and PROactive questionnaire data should be downloaded at day -9 and day 80 visits. A fully charged activity monitor and new 7 day daily PROactive instrument should be dispensed, and this data should be collected at baseline (day 1) and last dose (day 90) visits respectively.

The day -9 visit will also be used to familiarise participants with the home exercise training program, and to dispense equipment for home exercises, although participants should only begin exercises on day 1.

A practice incremental shuttle walk test (Section 9.2.3.2) should also be carried out at the day -9 visit to familiarise participants with the test prior to baseline.

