9.2.3.2. Shuttle walk tests (Incremental shuttle walk test and endurance shuttle walk test)

Participants will perform a practice standard, incremental shuttle walk test on the day -9 visit. An incremental shuttle walk will be performed at the baseline visit and the day 90 visit to determine peak work rate. After a minimum 40 minute rest, participants will perform constant work rate testing (endurance shuttle walk test) at 85% of peak work rate from the incremental walk test conducted at the baseline visit.

Tests will be stopped when participants are unable to maintain the walking speed and/or are too tired and/or breathless to continue [Singh, 1992]. The total distance walked from

the incremental test, duration in seconds from the CWR and percentage change for both peak work rate and endurance time should be recorded.

Site-specific training for this procedure will be given to harmonize data collection procedures prior to participant recruitment.

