### 5.2. Baseline Definitions

Parameter	Study Assessments Considered as Baseline			Baseline Used in Data Display
	Screening	Day -9	Day 1 (Pre-Dose)	
Efficacy				
Leg Strength	X		X	whichever is latest*
Incremental Shuttle Walk Test		X	X	whichever is higher
Endurance Shuttle Walk Test			X	Day 1
Dual-energy X-ray Absorptiometry (DXA)			X	Day 1
Short Physical Performance Battery (SPPB)	X		X	whichever is latest*
COPD Assessment Test (CAT)			X	Day 1
Patient Global Rating of Severity (PGRS)			X	Day 1
St George Respiratory			X	Day 1

Parameter	Study Assessments Considered as Baseline			Baseline Used in Data Display
	Screening	Day -9	Day 1 (Pre-Dose)	
Questionnaire COPD (SGRQ-c)				
PROactive Physical Activity	X	X		See detail below**
Spirometry	X		X	whichever is latest*
Sniff Nasal Inspiratory Pressure (SnIP)	X		X	whichever is latest*
Safety				
Vital Signs	X		X	whichever is latest*
12-lead ECG	X		X	whichever is latest*
Haematology	X		X	whichever is latest*
Clinical Chemistry	X		X	whichever is latest*
Urinalysis	X		X	whichever is latest*
hsCRP, Fibrinogen			X	Day 1
Lipid panel	X		X	whichever is latest*
PSA	X		X	whichever is latest*
HbA1c	X			screening
Exploratory				
Cardiac and liver MRI			X	Day 1
Handgrip strength	X		X	whichever is latest*
Reproductive Tissue Biomarkers			X	Day 1
Bone Biomarkers			X	Day 1
***Exploratory Biomarkers			X	Day 1
***Monitored home exercise program		X	X	whichever is latest*

\*Baseline value will be the latest pre-dose assessment with a non-missing value, including those from unscheduled visits. If time is not collected, Day 1 assessments are assumed to be taken prior to first dose and used as baseline.

\*\*Baseline will be the average of the data collected from the 7-day period after Day -9 device dispense.

\*\*\*Exploratory Biomarkers and home exercise program will be analysed separately and will not be reported as part of this study Statistical Analysis Complete reporting.

Unless otherwise stated, if baseline data is missing no derivation will be performed and baseline will be set to missing.

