
 
• Treatment difference (GSK2881078 – placebo) in the change from baseline and percentage change from baseline at Day 90 will be analysed using ANCOVA where baseline and treatment will be included as the independent variables in the model. Each gender will be analysed separately. The analyses will be based on the analysis population for the endpoints CWR duration, peak performance from incremental shuttle walking test and SGRQ total score additionally the endpoints CWR duration and SGRQ total score will be analysed for per-protocol population as well.
 
• If there are any departures from the distributional assumptions, the change of log-transformed data at post- baseline from log baseline will be the response variable, adjusted for treatment, and log-transformed baseline value.
 
• A Bayesian approach will also be conducted to estimate the treatment difference in the change from baseline at Day 90 for CWR duration and change from baseline SGRQ total score for the analysis population, following the similar procedures described in Section 7.1.4.1. for the primary efficacy endpoint analysis with the model being constructed as below:
 
• Create indicator variables for the categorical effect: Treatment (GSK2881078 vs. Placebo). For treatment, if treatment=placebo, then drug=0; if treatment=GSK2881078, then drug=1;
 
• For subject i on treatment j, the model can be written as:  <math display="block">CH_{ij} = \beta_0 + \beta_1 \text{ drug} + \beta_2 \text{ base} + \epsilon_{ij}</math>                     where CH refers to the change from baseline at Day 90; base means baseline assessment; drug=0 when treatment is placebo and drug=1 for GSK2881078 treatment; <math>\epsilon_{ij} \sim N(0, \sigma^2)</math>; <math>\beta_1</math> is the estimated treatment difference (GSK2881078 vs. placebo) at Day 90;
 
• Set seed=123456 with the simulation size of 200000 and 5000 burn-in iterations; the sample size and the number of burn-in iterations could be updated during the convergence check.
 
• The non-informative priors (normal (0, var=1e6)) will be used for the regression parameters <math>\beta_0</math>, <math>\beta_1</math>, and <math>\beta_2</math>. and the prior for variance <math>\sigma^2</math> will be the inverse gamma (0.01, scale=0.01)
 
• For calculating the posterior adjusted least square mean and corresponding difference, use the coefficient of L-matrix of the covariates from the corresponding ANCOVA analysis
 

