**Model Results Presentation**

- For change and percent change from baseline, adjusted means and corresponding standard error of means (SEs) and 90% confidence intervals will be presented for each treatment at Day 90, together with estimated treatment differences (GSK2881078 – Placebo) and the corresponding 90% confidence intervals through ANCOVA model.
- In case of the violation of assumptions in ANCOVA analysis, adjusted mean for ratio to baseline and 90% confidence intervals will be presented for each treatment by gender, together with adjusted treatment ratio of the ratio (postbaseline value/baseline value) between the two treatments with the corresponding 90% confidence interval be presented.
- For the Bayesian analysis, n, posterior adjusted least square mean and 90% highest posterior density (HPD) interval, the adjusted treatment difference and its 90% HPD credible interval and standard deviation for the posterior adjusted least square mean and difference will be reported along with the estimated probabilities.
- For the Bayesian analysis for CWR duration, the probability of treatment difference (GSK2881078-placebo) greater than 36 seconds and less than 48 seconds will be estimated through the simulations of the posterior probability distribution. Similarly, for the Bayesian analysis for SGRQ total score, the probability of treatment difference (GSK2881078-placebo) greater than 2 points and less than 4 points will be estimated through the simulations of the posterior probability distribution.

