## 12.3. Appendix 3: Assessment Windows

### 12.3.1. Definitions of Assessment Windows for Analyses

Analysis Set / Domain	Parameter (if applicable)	Protocol Window		Target	Analysis Window		Analysis Timepoint
		Beginning Timepoint	Ending Timepoint		Beginning Timepoint	Ending Timepoint	
All	All	Day -30	Day -11	Day -30 to -11	Day -60	Day -12	Screening/Visit 1
All	All	Day -11	Day -7	Day -9	Day -11	Day -5	Visit 2
All	All	Day -2	Day 1	Day 1	Day -4	Day 1	Visit 3, Day 1
All	All	Day 12	Day 16	Day 14	Day 10	Day 18	Visit 4, Day 14
All	All	Day 24	Day 32	Day 28	Day 22	Day 34	Visit 5, Day 28
All	All	Day 52	Day 60	Day 56	Day 50	Day 62	Visit 6, Day 56
All	All	Day 76	Day 84	Day 80	Day 76	Day 84	Visit 7, Day 80
All	All	Day 85	Day 91	Day 90	Day 85	Day 97	Visit 8, Day 90
All	All	Day 126	Day 140	Day 132	Day 126	Day 140	Follow-Up, Day 132

- For scheduled visits the analysis visit would equal the nominal visit irrespective of the assessment date and irrespective of whether that date falls in the visit window.
- Only unscheduled visits are slotted according to the table above and this slotting algorithm will be applicable for both efficacy and safety domains.
- After slotting of Un-scheduled visits, if there are multiple assessments at a planned timepoint, then the value closest to the target day for that window will be considered. If the multiple assessments are equidistant from the target day, then mean of the assessments will be considered.
- For any time post baseline and baseline (if the definition of baseline is the latest pre-dose visit) all assessments are used irrespective of whether they fall into visit windows or not.

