## 12.6. Appendix 6: Derived and Transformed Data

### 12.6.1. General

Multiple Measurements at One Analysis Time Point

 
• Mean of the measurements (not in case of visit slotting) will be calculated and used in any derivation of summary statistics but if listed, all data will be presented.
 
• If there are two values within a time window (as per Section 12.3.1) the value closest to the target day for that window will be used. If values are the same distance from the target, then the mean will be taken.
 
• Participants having both High and Low values for Normal Ranges at any post-baseline visit for safety parameters will be counted in both the High and Low categories of “Any visit post-baseline” row of related summary tables. This will also be applicable to relevant Potential Clinical Importance summary tables.
 

Study Day

 
• Calculated as the number of days from First Dose Date: 
 
• Ref Date = Missing → Study Day = Missing
 
• Ref Date < First Dose Date → Study Day = Ref Date – First Dose Date
 
• Ref Date ≥ First Dose Date → Study Day = Ref Date – (First Dose Date) + 1
 
 
 
 
Note that Treatment Start Date is considered as Study Day 1.

Post-baseline

 
• Post-baseline refers to the combined time periods of On-treatment and Post-treatment.
 

Change from Baseline
= Post-baseline - Baseline
Ratio to Baseline
= $\exp(\log(\text{Post-baseline}) - \log(\text{Baseline}))$
Percent Change from Baseline
= $100 * (\text{Post-baseline} - \text{Baseline}) / \text{Baseline}$
Treatment compliance

= <math>100 * (\text{Total Amount Taken} / (\text{Treatment duration in days} * 2))</math>
 
Total Amount Taken = Total tablets dispensed – Total tablets returned – Total tablets lost.

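### The ISWT baseline is the higher of two walks while Day 90 is a single walk, so per-arm ISWT changes read low relative to a Day 1 baseline; the treatment difference is not affected

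*SAP*

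**What the plan says.** SAP 5.2 (Baseline Definitions) sets the ISWT baseline from Day -9 and Day 1 as "whichever is higher". No other parameter in that table has this rule; most of those with two usable pre-dose assessments take the latest non-missing value. The footnote to Table 2.39 repeats it ("the highest non-missing pre-dose assessment from day -9 and day 1 is identified and captured as" a derived baseline visit), as does the shell for listing EFF_L6, so it is not a slip in one place.

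Protocol 9.1.2 gives the Day -9 walk a different role: it "should also be carried out at the day -9 visit to familiarise participants with the test prior to baseline". Protocol 9.2.3.2 then states: "An incremental shuttle walk will be performed at the baseline visit and the day 90 visit to determine peak work rate". That is one walk at each visit.

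No matching rule applies after baseline. Under SAP 12.3.1, once unscheduled visits are slotted, "if there are multiple assessments at a planned timepoint, then the value closest to the target day for that window will be considered", with the mean used for ties. The highest value is never taken.

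SAP 12.6.1 defines change as "Post-baseline - Baseline". Under SAP 7.2.4.1, change and percent change at Day 90 "will be analysed using ANCOVA where baseline and treatment will be included as the independent variables in the model", separately by sex. Beside the treatment difference, "adjusted means and corresponding standard error of means (SEs) and 90% confidence intervals will be presented for each treatment at Day 90". Table 2.39 adds descriptive change, percent change and ratio to baseline by arm.

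SAP Table 1, which lists departures from the protocol's analysis, does not mention the ISWT baseline rule, and no rationale is given elsewhere.

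**The concern.** The higher of two walks can never be shorter than the Day 1 walk. Subtracting it from a single Day 90 walk therefore gives each participant a change no larger than the change from Day 1, and a smaller one for anyone who walked further on Day -9. Test-to-test variation alone puts some participants in that group. With no true change at all, the mean change in both arms would tend to be negative.

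What is at stake is how per-arm results are read. Both arms follow a home exercise programme, so readers will look at the change within each arm. A modest true gain could be reported as little change or as a loss, with nothing in the tables to warn of it.

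**Working it through.** **Inputs from the documents.** Protocol 10.1.1 gives an SD of change in ISWT of 57 m, exploratory between-arm targets of 28.5 m or 47.5 m, and 20 evaluable participants per arm in each sex.

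**Inputs not in the documents, so assumed.** θ is the SD of the Day 1 minus Day -9 difference, taken from 14.25 to 57 m. d is the mean learning gain from Day -9 to Day 1, taken from 0 to 50 m. If each walk has independent noise with SD σ, then θ = σ√2. The top value, θ = 57 m, treats the whole of the stated change SD as test noise (σ = 57/√2 = 40.3 m).

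**Step 1: reproduce the plan's precision figure.** Half-width of the 90% CI = t(0.95, 2n−2) × 57 × √(2/n). This gives 44.20 m at n = 10 and 30.39 m at n = 20, against 44.2 and 30.4 m in the protocol. The 57 m is therefore being used as the per-arm SD of change.

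**Step 2: shift in the mean baseline.** With X1 the Day -9 walk and X2 the Day 1 walk, both normal,

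shift = E[max(X1, X2)] − E[X2] = θ·φ(d/θ) − d·Φ(−d/θ).

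- θ = 57, d = 0: 57 × 0.399 = 22.7 m.
- θ = 28.5, d = 20: 28.5 × 0.312 − 20 × 0.241 = 8.9 − 4.8 = 4.1 m.

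Downward shift in mean per-arm change (m):

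| θ (m) | d = 0 | d = 10 | d = 20 | d = 30 | d = 50 |
|---|---|---|---|---|---|
| 14.25 | 5.7 | 2.0 | 0.5 | 0.1 | 0.0 |
| 28.5 | 11.4 | 7.1 | 4.1 | 2.1 | 0.5 |
| 40.3 | 16.1 | 11.6 | 8.0 | 5.3 | 2.1 |
| 57 | 22.7 | 18.1 | 14.1 | 10.8 | 6.0 |

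The shift falls towards zero as learning dominates noise, but it never changes sign.

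**Step 3: check through the planned ANCOVA.** The simulation used 20 per arm, 4000 replicates, a true change of 0 m on placebo and 28.5 m on active, and an assumed walking distance with mean 300 m and between-person SD 80 m. Adjusted means (m):

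| θ, d | Day 1 baseline: placebo / active / difference | Higher-of-two baseline: placebo / active / difference |
|---|---|---|
| 28.5, 0 | 0.19 / 28.50 / 28.31 | −11.17 / 17.17 / 28.34 |
| 28.5, 20 | 0.10 / 28.49 / 28.39 | −3.98 / 24.45 / 28.42 |
| 57, 0 | −0.07 / 28.89 / 28.96 | −22.79 / 6.12 / 28.92 |
| 57, 20 | 0.06 / 28.36 / 28.30 | −14.06 / 14.36 / 28.41 |

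Both arm means move down by the step 2 amount. The difference between arms does not move.

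**Step 4: what best-of-two buys.** The higher of two walks is a less noisy covariate than one walk. Simulation put the SE of the treatment difference about 1 to 8% larger with Day 1 alone. As a check, take no learning and test noise small beside between-person spread. The residual variance is then 2σ² from Day 1, against σ² + σ²(1 − 1/π) = 1.68σ² from the higher of two, and √(2/1.68) = 1.09. The loss of precision is a single-digit percentage.

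**The case against.** The strongest reply is that no planned inference is touched. The ISWT summary measure in SAP 7.2.2 is the adjusted treatment difference. Both pre-dose walks precede randomisation, so the shift cancels. Per-arm change cannot be attributed to drug or to exercise under either baseline, because there is no arm without exercise. ISWT is not among the decision-making endpoints in SAP 7.2.3, has no Bayesian threshold, and its tables are not headline results. The rule is also stated openly in SAP 5.2, and Table 2.39 and listing EFF_L6 would probably let a reader see the Day 1 values. All of this stands and limits the weight of the point. It does not make the reported per-arm means and intervals like for like.

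A second reply is that best-of-two deals with learning. It does so only in part. When participants improve after practice, Day 1 is already the higher walk and the rule does nothing. It acts only when Day -9 was higher, which is mostly favourable noise, and Day 90 has no equivalent protection.

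A reader might infer more than the documents support:

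- **That the treatment effect is biased.** It is not, on absolute change. The percent-change difference is only slightly rescaled by the larger denominator.
- **That the shift removes a fixed share of the 28.5 m target.** That target is a difference from placebo, where the shift cancels, so the ratio compares unlike quantities. There is also no support for a lower bound above zero.
- **That every participant's change is too low.** There is no shift for anyone whose Day 1 walk was at least as long, or who has only one pre-dose walk. Further learning between Day 1 and Day 90 would push change upward under either baseline, so the net error against true change is unknown.
- **That the endurance walk analysis is compromised,** because its speed comes from the baseline-visit ISWT. The endurance walk has its own Day 1 baseline and its own ANCOVA, and no planned model uses the ISWT baseline with it.

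**Conclusion.** The point holds as one about per-arm reporting. The baseline rule is asymmetric with Day 90, departs from the protocol's description of Day -9 as practice, and is not declared in SAP Table 1. Whether Table 1 had to list it is arguable, since protocol section 10 gives no ISWT baseline derivation. Relative to a Day 1 baseline, mean per-arm change is lowered by about 0 to 23 m in both arms and both sexes, and percent change and ratio to baseline fall with it. The range rests on assumed values of θ and d and on normal, independent test noise. The top end needs all of the 57 m SD to be noise and no learning, which is unlikely given that the Day -9 walk exists to familiarise participants. The direction needs only that some participants walked further on Day -9. The treatment difference in absolute change is sound. This is a low-cost improvement to a secondary endpoint's tables and does not threaten the trial's conclusions.

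**What to change.** 1. Add the ISWT baseline rule, with its rationale, to SAP Table 1.
2. In Tables 2.37 to 2.39, add per-arm change and percent change from the Day 1 walk, using Day -9 only if Day 1 is missing. State that fallback in SAP 5.2, because the protocol does not give one.
3. Footnote the existing rows: change from the best-of-two baseline is shifted downward relative to change from Day 1.
4. Keep the best-of-two baseline in the ANCOVA for the treatment difference. Moving that model to Day 1 would slightly widen its interval (step 4). The sponsor's team may also see unblinded functional data during the study, so adding a summary is safer than replacing a prespecified rule.

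The cost is one extra derivation and a few table rows. No new data are needed and no other endpoint changes.
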